**Appendices**

**Appendix A – MBSR protocol**

**Appendix B – MBCT protocol**

## 1.0 Background

### ABSTRACT

The state of mindfulness can be described as a form of meta-awareness in which attention is allocated to the present moment of external and internal sensory or mental experience, without reactivity, and without dwelling on any particular sensory or mental object with judgement or evaluation. Mindfulness-based Interventions (MBIs) are a family of standardized cognitive and behavioral therapies that focus on cultivating mindfulness-related skills for improving maladaptive cognitive, emotional, and behavioral processes.

This mixed methods pilot study proposes to investigate proposed neurobiological, physiological, psychosocial-behavioral, and cognitive mechanisms by which MBIs may improve health outcomes. Target (mechanism) engagement is expected to facilitate identification of individuals who are most likely to benefit (or not) from MBIs and further develop targeted interventions for optimization of delivery. Although there are very specific aims and hypotheses to be tested, this preliminary exploratory investigation will provide feasibility data and allow for refining existing hypotheses for larger research proposals to be submitted for extramural grant support.

### BACKGROUND & RATIONALE

On closer analysis, mindfulness has been more clearly operationalized as “the continuous discriminative attentional capacity for encoding and recollecting experiences efficiently—without forgetfulness or distraction, and in the appropriate context”. From a cognitive perspective, it can be conceptualized as a state of meta-awareness in which attention is allocated to the present moment of external and internal sensory or mental experience, without reactivity, and without dwelling on any particular sensory or mental object with judgment or evaluation. Through cultivation of this state of meta-awareness, it is believed that multiple other skills are developed. These skills have been described as six fundamental mechanisms by which mindfulness functions (Vago and Silbersweig 2012):

- **1) Intention & Motivation**
  - Effortful to Effortless
  - Self-focused to Other-focused
- **2) Attention Regulation**
  - Sustained Attention, control, & flexibility (engagement, disengagement),
  - Meta-awareness (de-centering & executive monitoring)
- **3) Emotion Regulation**
  - Equanimity,
  - Inhibitory control
- **4) Extinction and Reconsolidation**
  - Mental habits & biases shifted toward adaptive trajectories
- **5) Prosociality**
  - Empathy, Theory of Mind, & Altruistic Behavior
- **6) Sensory Clarity**
  - Embodied cognition

## Contemplative Neuroscience & Integrative Medicine Laboratory

Despite successful medication and psychotherapies, stress-related health problems, pain outcomes, and psychopathologies rarely respond completely and are not always cost-effective. MBI's offer a low-cost, non-pharmacological alternative with a growing evidence-base.

A major challenge in improving treatment response and overall outcome in patients with high levels of stress or psychopathology, who are well characterized with mild to moderate severity, and whose residual symptoms are not addressed with a potentially effective medication for an adequate length of time lies within

- (1) identifying and testing the neurobiological, behavioral, and psycho-social mechanisms by which symptom reduction occurs and
- (2) identifying and testing a particular clinical endophenotype of individuals who may (or may not) benefit from augmentation through a mindfulness-based intervention

### **Mindfulness-based Interventions (MBIs)**

Mindfulness-based Stress Reduction (MBSR). (see Appendix A) Mindfulness-Based Stress Reduction (MBSR) is a well-defined and systematic patient-centered educational approach which uses relatively intensive training in mindfulness meditation as the core of a program to teach people how to take better care of themselves and live healthier and more adaptive lives. The prototype program was developed at the Stress Reduction Clinic at the University of Massachusetts Medical Center. This model has been successfully utilized with appropriate modifications in a number of other medical centers, as well as in non-medical settings such as schools, prisons, athletic training programs, professional programs, and the workplace.

We emphasize that there are many different ways to structure and deliver mindfulness-based stress reduction programs. 8-week MBSR treatment protocol(Kabat-Zinn 1982) is standardized and incorporates mindfulness skills into meditation training and self-inquiry to assist people with stress, pain and a range of conditions and life issues that were initially difficult to treat in a hospital setting. The group intervention entails weekly group meetings (two-hour classes) and a one-day retreat (six-hour mindfulness practice) between sessions six and seven, homework (45 minutes daily), and instruction in three formal techniques: mindfulness meditation, body scanning and simple yoga postures.

- a) Group Pre-program Orientation Sessions (2.5 hours) followed by a brief individual interview (5-10 minutes)
- b) Eight-weekly classes 2.5-3.5 hours in duration
- c) An all-day silent retreat during the sixth week of the program (7.5 hrs)
- d) "Formal" Mindfulness Meditation Methods:
  - Body Scan Meditation - a supine meditation
  - Gentle Hatha Yoga - practiced with mindful awareness of the body
  - Sitting Meditation - mindfulness of breath, body, feelings, thoughts, emotions, and choiceless awareness
  - Walking Meditation
- e) "Informal" Mindfulness Meditation Practices (mindfulness in everyday life):
  - Awareness of pleasant and unpleasant even
  - Awareness of breathing

## Contemplative Neuroscience & Integrative Medicine Laboratory

- Deliberate awareness of routine activities and events such as: eating, weather, driving, walking, awareness of interpersonal communications

f) Daily home assignments including a minimum of 45 minutes per day of formal mindfulness practice and 5-15 minutes of informal practice, 6 days per week for the entire duration of the course

g) Individual and group dialogue and inquiry oriented around weekly home assignments including an exploration of hindrances to mindfulness and development and integration of mindfulness-based self-regulatory skills and capacities

h) Incorporation of exit assessment instruments and participant self-evaluation in Class 8

- Total in-class contact: 30+ hours
- Total home assignments: minimum of 42-48 hours
- Total group Orientation Session time: 2.5 hours

Mindfulness-based Cognitive Therapy (MBCT) (Appendix B). 8-week MBCT treatment protocol is standard as defined by Segal, Williams and Teasdale(Segal, Williams et al. 2013) with some minor modifications to address suicidality and presence of acute symptoms, i.e., introduction of crisis plans and cognitive components addressing suicidal cognitions and hopelessness. MBCT uses core meditation techniques (i.e., focused attention, open monitoring, body scan, breathing space, yoga) with a focus on mindful awareness as its core therapeutic ingredient and adds components of cognitive behavior therapy (CBT) (Segal, Williams et al. 2013).

### **8 x 120-minute weekly sessions**

SESSION 1: AWARENESS & AUTOMATIC PILOT

SESSION 2: DEALING WITH BARRIERS & LIVING IN OUR HEADS

SESSION 3: GATHERING THE SCATTERED MIND

SESSION 4: RECOGNIZING AVERSION & STAYING PRESENT

SESSION 5: ALLOWING/LETTING BE

SESSION 6: THOUGHTS ARE NOT FACTS

SESSION 7: HOW CAN I BEST TAKE CARE OF MYSELF?

SESSION 8: USING WHAT HAS BEEN LEARNED TO DEAL WITH FUTURE MOODS

## **2.0 Specific Aims**

Pre-Study Paradigm Testing: Before commencing the research delineated in this protocol, we will collect EEG and fMRI data from 30 healthy subjects between the ages of 18 and 55. This will allow us to test all of our experimental paradigms and make sure they are working properly prior to recruiting the patients for the research described in this protocol.

We propose to test candidate neurophysiological, behavioral, and psychosocial mechanisms by which MBIs improves outcomes in patients with high levels of 1) reported stress; 2) chronic pain; 3) clinical anxiety; 4) clinical depression with persistent residual symptoms. Specifically, we aim to:

- (1) Use fMRI to test whether fronto-limbic neural activation patterns mediating IC in the context of emotion are modulated by MBIs.

(2) **Aim 2: To examine the neurobiological markers of psychopathology, by investigating the neurophysiological substrates (EEG/ERPs) of working memory and executive function in depressed and anxious patients.**

a. (tested by the N-Back task). Lastly, post-MBCT or MBSR will facilitate improved cognitive processing with an emotional memory manipulation, i.e. high cognitive load, mood-incongruous (happy/positive) facial stimuli, indexed by increased amplitudes of N170, VPP, and P300 ERPs during relevant stimuli trials.

(3) **Aim 3: To determine whether an 8-week MBCT modifies P1 threat-related attentional bias markers in anxious patients.**

(4) **Aim 4: To investigate the relationship between P1 threat-related attentional bias markers, acute treatment response and durability in anxious patients enrolled in MBCT.**

(5) **Aim 5. Assess the role of sustained attention (i.e. vigilance) and inhibitory control as self-regulatory mechanisms predicting improvements on patient-reported outcomes for patients with high stress**

(6) **Aim 6. Assess effects of treatment type and the interaction with self-regulatory measures on clinical outcomes.**

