### **3.0 Inclusion/Exclusion Criteria**

Eligibility Criteria for Pre-Study Paradigm Testing:

- Before commencing the research delineated in this protocol, we will collect EEG and fMRI data from 30 healthy subjects to test all of our experimental paradigms and make sure they are working properly.
- Flyers and ResearchMatch will be used to circulate information about the study to the Vanderbilt campus and surrounding community.
- The subjects must be between the ages of 18 and 55.
- The 30 subjects will not complete the full pre-screening questionnaire, but will receive a phone screen to make sure they can safely participate in the EEG and fMRI protocol.

Eligibility Criteria Across All Study Arms:

- At prescreen, must be currently registered for MBCT or MBSR; at posttest, must have attended five of eight sessions for “completion”.
- Must possess English language skills sufficient for providing informed consent, completing questionnaires, and understanding instructions
- Age range: 18-55

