## 9.0 Statistical Considerations

**Power analysis.** Presently, no studies have explored P1 ERP activity in anxious populations before and after an MBCT intervention, so no direct estimation of effect size is available. However, Schoenberg et al. conducted a study in which ADHD-related ERP markers were monitored before and after an MBCT intervention. Therefore, mean amplitude differences and standard deviations from the study were used to determine the sample size for the proposed research. An a priori power analysis conducted using PASS version 11 software indicated that a minimum of 34 patients are needed to reject the null hypothesis with 80% power at a type I error rate of 0.05. Accounting for 18% attrition, 42 patients will be recruited in total for the Anxiety Arm.

A repeated-measure ANCOVA of pre- and post-treatment fMRI data will be performed to quantify the MBCT group and test Hypothesis 1(a) [*Target engagement will be identified through a significant interaction (post vs. pre-intervention; negative vs. neutral words; NoGo vs. Go) involving critical nodes of the fronto-parietal control network (dACC, FPC, AI) and decreased activation in limbic regions (hippocampus, amygdala)*]. A classical fixed sample trial design was conducted to determine a sample size that provides a Type I error of no more than 5% and a statistical power of no less than 80%. Based on the pre- and post-treatment fMRI brain imaging data of 10 borderline personality disorder patients for a design of 2 time points and 1 key condition contrast  $[(\text{Negative vs Neutral}) \times (\text{No-Go vs Go})]$  undergoing the same Go-NoGo Emotional Word paradigm we are using in this study) with the differential BOLD response **effect size at 1.963, and 0.274 for the 2 time points** observed in the right amygdala region (ROI with relatively small effect size), a sample size of no less than 25 (21 for a statistical power of no less

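### Aims 1 and 3 are worded as treatment effects, and Hypothesis 1(a) declares target engagement, from pre-post change in patients who all receive an MBI; condition-specific retest or time change cannot be separated from the MBI

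*Combined protocol and SAP*

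**What the plan says.** Two aims in section 2.0 ask about an effect of the intervention on a neural marker. Aim 1 is to "Use fMRI to test whether fronto-limbic neural activation patterns mediating IC in the context of emotion are modulated by MBIs". Aim 3, for the Anxiety Arm, is "To determine whether an 8-week MBCT modifies P1 threat-related attentional bias markers in anxious patients".

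Section 9.0 gives the fMRI analysis: "A repeated-measure ANCOVA of pre- and post-treatment fMRI data will be performed to quantify the MBCT group". The rule that goes with it, Hypothesis 1(a), is: "Target engagement will be identified through a significant interaction (post vs. pre-intervention; negative vs. neutral words; NoGo vs. Go", at named fronto-parietal nodes and with reduced limbic activation. The factors are time and two within-person task conditions. There is no treatment-group factor.

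For P1, section 9.0 gives only a sample size: "a minimum of 34 patients are needed to reject the null hypothesis with 80% power at a type I error rate of 0.05". It states no P1 model, test or attribution rule.

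On comparators, section 3.0 requires of every patient: "At prescreen, must be currently registered for MBCT or MBSR". Section 4.0 has Randomization in its title but describes no allocation. The 30 healthy subjects have another purpose: "This will allow us to test all of our experimental paradigms and make sure they are working properly". They are not described as controls or as retested at 8 weeks.

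**The concern.** A single-group pre-post change is the sum of whatever the MBI does and whatever would have happened anyway: practice on a repeated task, habituation to the stimuli, and natural recovery in people who entered with symptoms. Without patients tested twice over the same interval and not treated, or a second baseline, the two parts cannot be separated. The 5% error rate covers chance variation around zero change. It does not cover a real change with another cause.

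The wording matters because the Abstract in section 1.0 expects target engagement to help identify who benefits from MBIs, and says the pilot will refine hypotheses for larger grant proposals. If the Hypothesis 1(a) rule is followed as written, a retest effect that differs by task condition would go forward as evidence of mechanism.

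**Working it through.** **1. Is there a comparator for Aims 1 or 3?**
- Patients: all registered for MBCT or MBSR (section 3.0).
- Healthy subjects: paradigm testing before the study only (sections 2.0 and 3.0).
- Aim 6: compares treatment types, but on clinical outcomes, with self-selected programmes and no untreated arm.
- Repeat baseline or test-retest run: none described.

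So neither aim has one.

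**2. What does the Hypothesis 1(a) contrast remove?** Write the contrast at each visit as C = (Negative NoGo − Negative Go) − (Neutral NoGo − Neutral Go). The test is on C(post) − C(pre).
- A shift *a* added to all four cells at post contributes (a − a) − (a − a) = 0, so common drift cancels.
- A shift *b* in the Negative NoGo cell alone contributes (b − 0) − (0 − 0) = b, so condition-specific drift stays in full.

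**3. The plan's own figures.**
- Anxiety Arm recruitment: 34 / (1 − 0.18) = 41.46, rounded up to 42. This matches. The 34 itself cannot be re-derived, because the mean difference and SD behind it are not given.
- fMRI: the stated 21 per group for 80% power reproduces as a two-group comparison. Inputs from section 9.0 are effect sizes 1.963 and 0.274 at the two time points and a reduction of at most 40% in a PE group. SD 1 is my assumption. Difference = 1.963 × (1 − 0.40) − 0.274 = 1.1778 − 0.274 = 0.904. A two-sided 5% two-sample t-test has power 79.5% at 20 per group and 81.5% at 21. At 25 per group, the larger number in the text, power is 87.9%.

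Two groups of 21 make 42 evaluable patients, and two of 25 make 50. The Depression Arm is one group of 26, and the PE group is defined nowhere. The power text therefore appears to size a controlled comparison that the design does not contain.

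**4. Illustration of what drift would do.** The documents give no drift figure, so I take a range. Assume no MBI effect and a drift of d SDs of the change in the tested contrast. For the fMRI row this means drift in C, the part that survives step 2. For the P1 row I assume a paired test, since none is specified.

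Probability of significance in the drift direction = P(T > t(0.975, n − 1)), where T is noncentral t with n − 1 degrees of freedom and noncentrality d√n. The critical values are 2.035 for n = 34 and 2.060 for n = 26.

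| Assumed drift d | n = 34 (evaluable, P1) | n = 26 (recruited, fMRI) |
|---|---|---|
| 0 | 2.5% | 2.5% |
| 0.1 | 8.2% | 7.1% |
| 0.2 | 20.4% | 16.4% |
| 0.3 | 39.7% | 31.2% |
| 0.4 | 62.0% | 50.0% |

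For example, at n = 34 and d = 0.3 the noncentrality is 0.3 × √34 = 1.75. The two columns are not on the same footing: 34 is evaluable, 26 is recruited, and fewer evaluable scans would lower the second column.

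A simulation (40,000 replicates) gave two-sided rates of 40.0% at drift 0.3 and 81.3% at drift 0.5 with n = 34. A concurrent comparison of 17 and 17 with the same drift in both groups stayed at 4.9–5.0%.

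**The case against.** The strongest reply is that Hypothesis 1(a) is not a bare before-after test. It requires an interaction with valence and response inhibition, at named regions and with a stated limbic direction, so general practice or scanner-session effects drop out. That stands, and it narrows the point to condition-specific change. It does not remove it, because faster habituation to negative than to neutral words would produce exactly this interaction.

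A reader might infer that the plan turns any significant post-minus-pre difference, including one in P1, into target engagement. The documents do not support that. The term belongs to Hypothesis 1(a) and the Abstract and is never applied to P1, and Aim 3 has no decision rule. What remains for Aim 3 is the causal verb.

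The size of any drift is assumed. The documents also do not say whether post-test stimuli are the same or alternate sets, so habituation is plausible rather than shown. Some time effects are limited by the month of stable medication and the exclusion of recent regular meditation (section 3.0), the weekly treatment check-in (section 5.0) and the termination criteria (section 8.0). These help with outside treatment, not with retesting or natural recovery.

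Finally, this is a declared exploratory pilot, and an uncontrolled pilot is legitimate. That softens the consequence. But section 1.0 also says there are specific hypotheses to be tested, and section 9.0 sizes them at 80% power and 5% error. The pilot label does not license the attribution.

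**Conclusion.** The point holds in limited form. The analyses described can show that a marker changed between the two visits. They cannot show that the MBI changed it. For Aim 1 this affects the wording and the Hypothesis 1(a) rule, through condition-specific drift only; for Aim 3 it affects the wording only.

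The 20–62% and 16–50% figures are conditional on no MBI effect and on an assumed drift of 0.2 to 0.4 SD of the change in the tested contrast. They should not be read as the trial's actual false-positive rate, which the documents do not allow anyone to calculate. Nor does the point imply that the pilot must add a control group.

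The mismatch in the fMRI power text needs no drift assumption. With SD 1 assumed, the stated 21 per group matches a comparison against a PE group, and the single Depression Arm of 26 has no such group.

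**What to change.** 1. Reword Aims 1 and 3 and the Hypothesis 1(a) rule as change from pre- to post-MBI.
2. State that a significant change will not by itself be attributed to the MBI or called target engagement, and that attribution needs a controlled study.
3. Reconcile the fMRI power text in section 9.0: define the PE group and say where it comes from, or replace the calculation with one for a single group measured twice.

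Do not add a regression of change on attendance or home practice as support for attribution. Attendance is range-restricted, because completion needs five of eight sessions (section 3.0) and missing more than half leads to termination (section 8.0). Home practice is self-selected. Neither separates treatment from time, and a positive slope would encourage the causal reading.

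The cost is a text change and one revised power paragraph, with no new patients or visits. The downside is a weaker claim.

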### **3.0 Inclusion/Exclusion Criteria**

Eligibility Criteria for Pre-Study Paradigm Testing:

- Before commencing the research delineated in this protocol, we will collect EEG and fMRI data from 30 healthy subjects to test all of our experimental paradigms and make sure they are working properly.
- Flyers and ResearchMatch will be used to circulate information about the study to the Vanderbilt campus and surrounding community.
- The subjects must be between the ages of 18 and 55.
- The 30 subjects will not complete the full pre-screening questionnaire, but will receive a phone screen to make sure they can safely participate in the EEG and fMRI protocol.

Eligibility Criteria Across All Study Arms:

- At prescreen, must be currently registered for MBCT or MBSR; at posttest, must have attended five of eight sessions for “completion”.
- Must possess English language skills sufficient for providing informed consent, completing questionnaires, and understanding instructions
- Age range: 18-55

## Contemplative Neuroscience & Integrative Medicine Laboratory

- If currently taking maintenance anti-depressant and/or anti-anxiety medication, must have a "stable" regimen as indexed by no medication or dosage changes within the past month
- No prior diagnosis of bipolar I, bipolar II, psychotic personality disorder, borderline personality disorder, and/or narcissistic personality disorder
- No current history ( $\leq 6$  months) of substance abuse/dependence
- No current history ( $\leq 6$  months) of regular meditation practice ( $>1$  session/week;  $>10$  min/session)
- No history of medical illness associated with possible changes in cerebral tissue or cerebrovasculature (e.g., stroke) or with neurologic abnormality (e.g., seizure disorder, cerebrovascular or neoplastic lesion, neurodegenerative disorder, or significant head trauma, defined by loss of consciousness of  $\geq 5$  minutes)
- No current suicidal ideation

*Depression Arm (consists of fMRI scan, EEG with behavior, and self-report measures at pre- and post-treatment testing)*

- Beck Depression Inventory-II (BDI-II) score  $\geq 14$  (an indicator of depressive symptoms of mild to high severity)
- No fMRI contraindications: pregnancy, claustrophobia, or presence of a ferromagnetic object, including orthodontic braces

*Anxiety Arm (consists of EEG with behavior, fMRI scan, self-report measures at pretest and posttest)*

- Diagnosed (via SCID-V Screener) with an anxiety disorder (i.e., generalized anxiety disorder, panic disorder, specific phobia)
- Score of  $\geq 40$  on the Trait subscale of the Spielberger State-Trait Anxiety Inventory (an indicator of anxious symptoms of moderate to high severity)

*Stress Arm*

- Moderate to high stress is necessary for inclusion on behavioral testing/self-report
- Scores on PSS pre-screen  $> 14$  would be considered moderate to high perceived stress.

*Blood Draws (consists of a 10-mL draw at pre-treatment baseline and post-treatment testing; optional for depression/anxiety arm participants)*

Eligibility Criteria:

- At least 110 pounds
- Generally healthy by self-report on day of collection (i.e., free of cold and flu symptoms on the day of collection, no infections within two weeks prior to collection, no known sickle cell disease)
- Including the study draw, blood donation for clinical or research purposes within the preceding eight weeks will not exceed 550 mL
- No more than one blood draw will have occurred during the preceding week

*fMRI and EEG exclusion criteria*

